8.2 Populations for Analyses

- All Enrolled Data set: subjects who signed informed consent and registered in the study.
- All Treated Data set: all subjects who received at least one dose of either study drug.
- Response-Evaluable Data Set: all treated subjects who receive either study drug, have a baseline tumor assessment with measurable disease, and one of the following:
 - at least one evaluable on-treatment tumor assessment prior to subsequent therapy,
 - clinical progression prior to subsequent therapy, or
 - death, if death occurs within 100 days after last dose.
- Urelumab Pharmacokinetic Data Set: all subjects who receive at least one dose of urelumab and have adequate serum concentration data for urelumab PK.
- Nivolumab Pharmacokinetic Data Set: all subjects who receive at least one dose of nivolumab and have adequate serum concentration data for nivolumab PK.
- Urelumab Immunogenicity Data Set: all subjects who receive at least one dose of urelumab with baseline and at least one post-baseline urelumab ADA assessment available.
- Nivolumab Immunogenicity Data Set: all subjects who receive at least one dose of nivolumab with baseline and at least one post-baseline nivolumab ADA assessment available.
- Biomarker Data Set: all treated subjects who have evaluable biomarker data available.

8.3 Endpoint Definitions

Safety is the primary endpoint in this Phase 1/2 study. All subjects who receive at least one dose of urelumab or nivolumab will be evaluated for safety as measured by the occurrence of adverse events, serious adverse events, deaths and laboratory abnormalities, assessed during treatment and for 100 days in follow-up.

8.3.1 Primary Endpoint(s)

The primary objective (to assess the safety and tolerability of urelumab given in combination with nivolumab and to identify dose limiting toxicities (DLTs) and the maximally tolerated dose (MTD) of the combination) will be measured by the following primary endpoints.

- a) Incidence of adverse events: all non-serious adverse events will be collected from Day 1 until 100 days after the subject's last dose of study drug or until they discontinue the study as per [Section 3.5](#). All serious adverse events must be collected from the date of the subject's written consent until 100 days after discontinuation of dosing or until they discontinue the study as per [Section 3.5](#).
- b) Incidence of clinical laboratory test abnormalities including hematology and serum chemistry, and thyroid panel abnormalities, assessed at specified time points as designated in the Time and Events [Section \(5.1\)](#).

Assessments will be based on adverse event reports and the results of vital sign measurements, electrocardiograms (ECGs), physical examinations, imaging studies, and clinical laboratory tests. Adverse events will be categorized using the most current version of the Medical Dictionary for Regulatory Activities (MedDRA); both AEs and laboratory tests will be graded using NCI CTCAE v4.0. All subjects who receive study drug therapy will be evaluated for safety as measured by the rate of adverse events (AEs), and serious adverse events (SAEs), and will be assessed during treatment and for 100 days in follow-up.

8.3.2 Secondary Endpoints

8.3.2.1 Efficacy Endpoints

The secondary objective of assessing preliminary anti-tumor activity will be based on endpoints described below using RECIST v1.1 and investigator assessed response per IWG criteria for lymphomas.

Best overall response (BOR) is the best response designation recorded between the start of the study treatment and the date of objectively documented progression based on RECIST v1.1 (or relapsed based on IWG) taking into account any requirement for confirmation, or the date of subsequent anti-cancer therapy, whichever occurs first in the study. CR or PR determinations included in the BOR assessment must be confirmed by a consecutive second (confirmatory) evaluation meeting the criteria for response that is performed at least 4 weeks after the criteria for response are first met. **When SD is believed to be the best response, it must meet a minimum SD duration of 49 days. Measurements must have met the SD criteria at least once after study entry.** The above will be determined based on tumor measurements occurring every 8 weeks during the Treatment period (Cycle 1 Day 1 through Cycle 6 Day 56), and at planned timepoints during the Clinical/Safety Follow-up period.

Study level endpoints used to assess this objective are defined as follows:

Objective response rate (ORR) is defined as the total number of subjects whose BOR is either CR or PR divided by the total number of subjects in the population of interest.

Duration of Response (DOR) computed only for subjects with a BOR of CR or PR is defined as the number of days between the date of first response and the subsequent date of objectively documented disease progression based on the criteria (RECIST v1.1) or relapse based on IWG, or death due to any cause, if death occurred within 100 days after last dose, whichever occurs first. If death is more than 100 days after last dose, then DOR is censored at the last tumor assessment date. For those subjects who remain alive and have not progressed or received subsequent therapy, duration of response will be censored on the date of last tumor assessment. Subjects who receive subsequent therapy will be censored at the start of subsequent therapy.

Progression-Free Survival Rate (PFSR) is defined as the probability of a subject remaining progression-free and surviving a specific length of time (eg, 24 weeks). The PFS for a given subject will be computed based on the number of days between the first dose of study drug and progressive disease, relapse, or death due to any cause, if death occurred within 100 days after last dose. The PFSR will be estimated using Kaplan-Meier methods. For those subjects who remain alive and have not progressed, PFS will be censored on the date of the last tumor assessment. Subjects who did not have any on study tumor assessment and did not die will be censored on the date of first dose of study medication. The above will be calculated based on tumor measurements occurring every 8 weeks during treatment and at planned timepoints during the Clinical/Safety Follow-up period.

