### 4.2 Secondary Endpoints

#### 4.2.1 Preliminary Antitumor Activity

Tumor assessments will be performed every 8 weeks ( $\pm$  1 week) during the treatment period (Cycle 1 Day 1 through Cycle 6 Day 56), and at planned timepoints during the clinical follow-up period. In addition, subjects who discontinue study drug for reasons other than progression will continue to have tumor assessments completed every 12 weeks for the first year and then continue to receive scans per standard of care guidelines for follow-up or at a minimum of every 6 months until disease progression or withdrawal of consent.

Changes in tumor measurements and tumor response will be assessed by the investigator using the Response Evaluation Criteria in Solid Tumors (RECIST) version 1.1 for subjects with solid tumors and using the revised International Working Group (IWG) Criteria for subjects with B-cell NHL and Follicular Lymphoma. Investigators will also report the number and size of new lesions that appear while on-study. Endpoints will be defined based on all available tumor assessments.

The following set of efficacy study-level endpoints will be used.

- **Objective Response Rate (ORR):** The total number of subjects whose best overall response (BOR) is either a complete response or partial response for solid tumors and complete remission or partial remission for B-cell NHL, divided by the total number of subjects in the population of interest. Hereafter, complete response for solid tumors and complete remission

for B-cell NHL will both be referred to as complete response (CR); partial response for solid tumors and partial remission for B-cell NHL will both be referred to as partial response (PR).

- Best Overall Response: The subject's best response designation over the study as a whole, recorded between the date of first study drug administration and the date of objectively documented progression or relapse per RECIST 1.1 or IWG, with subsequent confirmation, or date of subsequent anti-cancer therapy, whichever occurs first in the study.
  - ◆ A minority of subjects may continue treatment beyond confirmed progression or relapse, as described in Protocol Section 3.5.1. For these subjects, the BOR should be determined based on response designations recorded up to the time of the initial RECIST 1.1 defined progression or IWG defined relapse or progressive disease.

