  - ◆ Complete or partial responses in solid tumors may be claimed only if changes in tumor measurements are confirmed by a consecutive assessment meeting the criteria for response or remission and performed no less than 4 weeks (28 days) after the criteria for response were first met.
  - ◆ When stable disease (SD) is believed to be the best response, it must meet the protocol specified minimum time from baseline. Measurements must have met the SD criteria at least once after study entry. The minimum criteria for SD duration (8 weeks) must have been satisfied (considering the  $\pm 1$  week tumor assessment window, 49 days will be used to derive SD).
- **Median Duration of Overall Response (mDOR):** The significance of ORR is assessed by its magnitude and duration of response. DOR is computed only for subjects with objectively defined CR or PR, and is defined as the time from first response to the subsequent date of objectively documented disease progression based on the criteria (RECIST 1.1) or relapse based on IWG, or death due to any cause, if death occurred within 100 days after last dose, whichever occurs first. If death is more than 100 days after last dose, then duration of response is censored at the last tumor assessment date. Subjects who remain alive and have not progressed nor received subsequent therapy, will have their DOR censored on the date of their last tumor assessment. Subjects who receive subsequent therapy will be censored at the start of subsequent therapy.
- **Progression Free Survival Rate (PFSR) at Week X:** The proportion of subjects remaining progression free and surviving at X weeks, where X is a specific length of time, eg, 24 weeks, which will be determined by the data for each interim or final analysis and will be documented in the data presentation plan (DPP). The proportion will be calculated by the product-limit method (Kaplan-Meier estimate) which takes into account censored data.

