  - Progression Free Survival (PFS): The PFS for a subject is defined as the time from the date of first dose of study drug to the date of the first documented disease progression or relapse, or death due to any cause, if death occurred within 100 days after last dose. Clinical deterioration in the absence of radiographic evidence is not considered progression for the purpose of determining PFS. Subjects who die within 100 days after last dose without a reported prior progression will be considered to have progressed on the date of their death. Subjects who remain alive and have not progressed will be censored on the date of the last tumor assessment. Subjects who did not have any on

study tumor assessment and did not die within 100 days after last dose of study medication will be censored on the date of first dose of study medication.

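### PFS and DOR stop counting deaths 100 days after last dose: DOR censors later progression-free deaths, and PFS gives most of them no rule

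*Protocol*

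**What the plan says.** **Death as an event.** Protocol 8.3.2.1 uses the same condition for DOR and PFS: "death due to any cause, if death occurred within 100 days after last dose". SAP 4.2.1 repeats it for both.

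**DOR, later death.** The Protocol says "If death is more than 100 days after last dose, then DOR is censored at the last tumor assessment date". The SAP agrees: "If death is more than 100 days after last dose, then duration of response is censored at the last tumor assessment date". Both also censor DOR at the start of subsequent therapy.

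**PFS, censoring at the last scan.** Protocol: "For those subjects who remain alive and have not progressed, PFS will be censored on the date of the last tumor assessment". SAP: "Subjects who remain alive and have not progressed will be censored on the date of the last tumor assessment".

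**PFS, no on-study scan.** Protocol: "Subjects who did not have any on study tumor assessment and did not die will be censored on the date of first dose". The SAP instead censors at first dose anyone without a scan who did not die inside the 100-day window.

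**Which scans count.** For PFS, Protocol 8.3.2.1 uses the 8-weekly scans on treatment and those "at planned timepoints during the Clinical/Safety Follow-up period". The SAP says: "Endpoints will be defined based on all available tumor assessments". Protocol 3.1.4 and SAP 6.1.4 plan scans for subjects without progression up to 3 years from first dose.

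**Use.** SAP 7.5 reports median DOR, median PFS and PFS rates at time points such as Weeks 24 and 48, all by Kaplan-Meier.

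**The concern.** Death without documented progression is part of both endpoints. The Protocol defines the PFS rate as the probability of being progression-free and alive at a given time. A subject who has died fails that definition, yet the death need not count.

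Censoring the death at the last scan treats the subject as if still at risk of a later progression. That is informative censoring, and it can only make late DOR look better. For PFS the problem starts earlier: with no rule for these subjects, two programmers could produce different curves from the same data. The SAP also says that the importance of ORR is judged by its size and its duration, so DOR carries part of the efficacy message.

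**Working it through.** The documents give no figure for PFS or DOR size, so there is none to reproduce. The check compares the rules, then the dates, then an illustrative size.

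**1. Rules for a death more than 100 days after last dose, without progression**

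| Subject | DOR | PFS, Protocol | PFS, SAP |
|---|---|---|---|
| Has on-study scans | Censored at last scan | No rule: not an event, not alive | No rule: same reason |
| No on-study scan | Not applicable | No rule: the subject did die | Censored at first dose |

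These gaps come from the 100-day condition and from the restriction of last-scan censoring to living subjects. They hold whichever scans count. The scan window decides something else: whether a late progression counts when a late death does not. Under the SAP it does. Under the Protocol's PFS window, scans stop at about the Day 100 visit, so that imbalance largely disappears for PFS.

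For DOR, a responder who starts new therapy and dies late meets two censoring rules, and neither document says which takes precedence.

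**2. Dates, with doses on schedule** (six 8-week cycles, nivolumab on Days 1, 15, 29 and 43; Protocol 3.1.2)

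- Last dose: 5 × 56 + 43 = day 323.
- Last countable death: 323 + 100 = day 423, which is 423 / 7 = week 60.4.
- Three years: 3 × 365.25 = 1,095.75, about day 1096.
- For a subject who completes treatment, the period in which (under the SAP) progression counts and death does not is 1,095.75 − 423 = 672.75 days, or 61% of the 3 years.
- Week 24 (day 168): dose day 57 + 100 = 157, before the landmark; dose day 71 + 100 = 171, after it. A death before Week 24 is missed only if the last dose was day 57 or earlier.
- Week 48 (day 336): 225 + 100 = 325, before; 239 + 100 = 339, after. A death before Week 48 is missed only if the last dose was day 225 or earlier.

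Example: the Day 100 scan is clean on day 423 and the next scan is due 84 days later, on day 507. Progression seen on day 507 is an event under the SAP. A progression-free death on day 480 is censored at day 423 for DOR and has no rule for PFS.

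**3. Illustrative size**

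The inputs are assumptions. Event times are exponential, with 200,000 simulated subjects per scenario. Median time to progression or death is 6, 12 or 24 months. Progression-free deaths are 5%, 10% or 20% of first events. Median time to last dose is 3 or 8 months, capped at day 323. For PFS, late deaths are assumed to be censored at the last scan (the DOR rule), with all scans counted. Compared with counting every death:

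- Week 24 PFS rate: higher by at most about 0.5 points.
- Week 48 PFS rate: higher by about 0.2–2.4 points.
- Median of 12 months: becomes 12.1–13.1. Median of 24 months: becomes 24.6–28.0.

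For median DOR there is a simple ceiling. Let M be the true median and f the share of first events that are progression-free deaths. If every such death were censored, the hazard would fall by the factor (1 − f) and the median would become M / (1 − f), a rise of M × f / (1 − f):

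- M = 52 weeks: 52 × 0.05 / 0.95 = 2.7 weeks; 52 × 0.10 / 0.90 = 5.8 weeks.
- M = 104 weeks: 104 × 0.05 / 0.95 = 5.5 weeks; 104 × 0.10 / 0.90 = 11.6 weeks.

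The actual rise is smaller, because deaths inside the 100 days still count. In the simulation above, a 24-month median at f = 10% rose from 24.1 to at most 25.9 months, which is 1.8 × 30.4375 / 7 = 7.8 weeks.

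**4. Against sampling error**

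The 95% half-width for a rate of 50% with 40 subjects is 1.96 × √(0.25 / 40) = 15.5 points, well above 2.4. With 20 responders and a 52-week median to progression, the central 95% range of the estimated median DOR was about 25–91 weeks in an illustrative simulation.

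**The case against.** The DOR rule is explicit, set in advance and identical in both documents, so it can be called a choice rather than an error. The 100 days match safety follow-up. OS is analysed separately by Kaplan-Meier (Protocol 8.4.2; SAP 7.5), so late deaths are reported. The PFS figures above model a rule that the documents do not contain, and under the Protocol's scan window no upward PFS shift appears. Counting every death also has a cost: a subject who stops scans and dies much later is treated as progression-free until death, which can inflate PFS.

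Much of this stands. It limits the size and argues for sensitivity analyses. It does not rescue the rule: death is part of the endpoint, survival is followed for 3 years, and the distortion runs one way. The missing PFS rule needs writing whatever its size.

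A reader might draw stronger conclusions that the documents do not support:

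- *That the SAP's use of all scans is what loses the late deaths.* The 100-day condition and the limit to living subjects do that. The SAP's window adds only the imbalance with progression.
- *That the distortion is large.* Rises of 12–24 weeks in median DOR, or 4.9–7.3 points at Week 48, can be produced, but only if progression-free deaths are very common. With a 104-week median to progression and death medians of 100 to 400 weeks, the implied share is 104 / 204 = 51% down to 104 / 504 = 21%. For PFS, medians of 60 and 100 weeks imply 60 / 160 = 37.5%. Nothing in the documents supports such shares.

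**Conclusion.** The point holds as a defect in definition, with limited consequences. From the text alone, late progression-free deaths are censored in DOR and lack a rule in PFS when scans exist. The documents also differ on late deaths without scans and on which scans count for PFS.

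The direction is optimistic for late DOR. It is optimistic for late PFS only if those deaths are censored and the SAP's window is used. The size cannot be known from the documents. The illustrative shifts rest on the assumed death shares, and median DOR moves by more than a few weeks at 5–10% only when the true median is long, or when such deaths are more common.

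It should be fixed, but it does not threaten the trial's main decisions. A reader might infer that it affects the move to Stage 2. It does not: that gate is 4 responses in 20 subjects, and PFS and DOR do not enter it. Both are secondary and descriptive, and the trial has no formal hypothesis to test.

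**What to change.** In Protocol 8.3.2.1 and SAP 4.2.1:

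1. Define the PFS and DOR event as the first documented progression or relapse, or death from any cause, regardless of time since last dose.
2. Censor at the last scan only subjects who are alive and progression-free. Censor at first dose only subjects who are alive with no on-study scan.
3. Use one scan window, by aligning the Protocol's PFS text with the SAP's use of every scan.
4. Keep DOR censoring at subsequent therapy, and state that it takes precedence over a later death.
5. Add two sensitivity analyses: one that censors deaths following two or more missed scheduled scans and, for PFS, one that censors at subsequent therapy.

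The cost is wording in two documents, minor programming and a few extra tables. No new death-date collection is needed: SAP 7.5 already lists last dose, last known alive and death dates per subject. Late PFS and DOR will look slightly less favourable.

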8.3.2.2 Pharmacokinetics (PK)

Urelumab and nivolumab maximum concentration (Cmax [μ g/mL]), end of infusion concentration (Ceoinf), time to maximum concentration (Tmax [hr]), trough concentration (Ctrough [μ g/mL]), area under the curve (AUC[0-T] and AUC[TAU] [μ g.hr/mL]) will be evaluated using non-compartmental analysis in all study subjects. ([Table 5.5.1-1](#))

8.3.2.3 Immunogenicity

Occurrence of specific anti-drug antibodies to urelumab and nivolumab will be determined from measurements obtained at planned timepoints specified in [Table 5.5.1-1](#)).

Endpoints for the study are incidence rates of persistent positive ADA as well as neutralizing positive ADA from initiation of each drug treatment up to and including the follow-up period of the last study drug dosed. Based on recommendation from BMS Immunogenicity Council, Harmonization of Clinical Immunogenicity Reporting by an Initiative of the Therapeutic Protein Immunogenicity Focus Group of the American Association Pharmaceutical Scientists, and the FDA Guidance for Industry Immunogenicity Assessment for Therapeutic Protein Products, the following definitions will be applied:

ADA Status of a Subject:

- **Baseline ADA Positive Subject:** A subject with baseline ADA positive sample
- **ADA Positive Subject:** A subject with at least one ADA positive sample relative to baseline at any time after initiation of treatment during the defined observation time period.
- **ADA Negative Subject:** A subject with no ADA positive sample after the initiation of treatment

Definitions for potential ADA Status of a Sample (Baseline ADA Positive, ADA Positive, or ADA Negative), as well as sub-categories of ADA Positive Subject such as Persistent Positive, Only the Last Sample Positive, Other Positive and Neutralizing Positive will be provided in the statistical analysis plan (SAP).

[REDACTED]

[REDACTED]

[REDACTED]

[REDACTED]

8.4 Analyses

8.4.1 Demographics and Baseline Characteristics

Frequency distributions of gender and race will be tabulated. Summary statistics for age, body weight, and height will be collected, and Body Mass Index (BMI) will be derived.

8.4.2 Efficacy Analyses

Individual best overall response (BOR), duration of response and PFS will be listed using RECIST v1.1 and IWG criteria, as appropriate. BOR outcomes will be tabulated by disease type and treatment (eg, with a column for each dose/regimen combination). The objective response rate (ORR) and PFS rate (eg, at 24 weeks) and corresponding confidence interval will be provided by tumor type and treatment. The duration of response and PFS will be estimated by Kaplan-Meier (K-M) methodology by disease type, depending on data availability. PFS rates at 24 weeks will be similarly estimated, based on K-M methodology. ORR, duration of response and PFS analyses will include subjects in the cohort expansion phase and subjects in dose escalation matching those in cohort expansion by disease type and treatment. Individual changes in the tumor burden over time may be presented graphically within a disease type. Landmark overall survival will be assessed as part of exploratory efficacy analysis, using Kaplan-Meier plots and the median (as measured using Kaplan-Meier Method) for each tumor type.

